# 3.4 Maximum Tolerated Dose (MTD) Definition

In the dose escalation phase for the combination of M6620 and avelumab, patients will be assigned sequentially in groups of up to 6 patients at each dose level. Three to 6 patients will initially be enrolled at each dose level for DLT observation. A total of 6 patients will be enrolled at each dose level in the event that a DLT is observed in 1 of the first 3 patients and/or additional safety data are needed.

The MTD is defined as the highest dose level with less than 2 patients with DLT out of at least 6 patients at the dose level. Management and dose modifications associated with adverse events are outlined in subsequent protocol sections.

The DLT assessment window is 28 days (1 cycle). In the absence of DLTs, patients may continue consecutive treatment. For patients who experience a DLT, they may continue treatment with modifications if the toxicity resolves and at the discretion of the treating physician and the Pl. In the absence of clinical deterioration and if the investigator believes that the patient continues to receive benefit from the treatment, patients may continue to receive study drug(s) after the first indication of progressive disease until a confirmatory scan is obtained.

To understand and safeguard against potential cumulative toxicities the study team will continue to monitor the occurrence of study drug related SAEs and AEs throughout the treatment period and during potential treatment extensions to allow for dose correction in the event of cumulative immune-mediated toxicities.

[figure not shown]
Delayed onset of significant toxicities will be evaluated on a case-by-case basis at the discretion of the PI in consultation with the Safety Monitoring Committee (SMC). At minimum, a review and discussion of potential delayed onset of significant toxicity will take place at review prior to a dose escalation decision.

### 3.5 Dose Escalation and Stopping Rules

The decision to proceed to the next dose level will be made after the first 3 patients in a dose level have completed 28 days (1 cycle) of dosing. Prior to advancing/changing dose levels, a dose

level summary will be completed and submitted to SMC for review and approval. The data discussed at the SMC during escalation/expansion phases and the minutes of the meetings will be submitted to the IND Office Medical Affairs & Safety group.

Figure 4: Dose Escalation Rules:

Dose escalation will occur at the planned dose levels until the MTD is determined. The MTD is defined as the highest dose level with less than two patients with DLT out of at least six patients. The recommended phase 2 dose (RP2D) will be based on the safety and preliminary efficacy data from the dose escalation and dose expansion arms. Intra-patient dose escalation will only be allowed if the patient experienced grade ≤1 AEs at the current dose.

All enrolled participants will be considered in the DLT analysis. If any patient should be excluded from the analysis, the reason(s) should be clearly documented (see Section 3.3). If a DLT occurs at a dose level with 3 patients within the first 28 days, 3 additional patients will be enrolled at that dose level. If at any time, at least one third of the participants at a dose level (33%) experience DLTs, the MTD will be reassessed and the next lowest dose level will be considered the MTD.

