- 16. M6620 may be administered to patients in the dose escalation phase at 1 of 3 doses: 240 mg/m² (dose level 1), 480 mg/m² (dose level 2), or 120 mg/m² (dose level -1) IV weekly, starting on Cycle 1 Day 1 (Days 1, 8, 15, and 22 of every cycle). M6620 will be administered to patients in the dose expansion phase of at the recommended phase 2 dose (RP2D) established in the dose escalation phase.
- 17. When M6620 and Avelumab are to be administered on the same day (e.g. C1D1, C1D15), avelumab will be infused first, with an interval of at least 1 hour before infusion of M6620.
- 18. CT, MRI, or PET-CT scans will be performed at screening, and then every 2 cycles or 8 weeks (± 7 days) for the first year of treatment. Thereafter, tumor assessments will be performed every 3 cycles or 12 weeks (± 7 days) independent of cycle delays. Confirmatory scans will also be obtained ≥ 4 weeks following initial documentation of objective response (OR) or progression of disease (PD). The type of scan obtained is at the discretion of the investigator as appropriate for the disease. However, the same method should be used for the duration of the study. Baseline brain CT or MRI scan is required for all high risk patients (such as breast, melanoma and other cancer types as determined by the PI/sub I) at baseline (screening). Patients with stable brain metastases present at baseline (screening) will have brain CT or MRI scans performed at each tumor assessment. If bone metastases are present at baseline (screening), then repeat bone imaging is required every 8 weeks for the first 52 weeks of study treatment and every 24 weeks thereafter. Bone imaging is required at the time of confirmation of CR for patients who have bone metastases.
- 19. Relevant tumor markers (e.g., CA125, PSA, and CEA) will be assessed at screening, and on Day 1 of every cycle (± 7 days) this will include blood draws at EOT and Long Term Follow-up.
- 20. One tumor biopsy is mandatory (C1D15), although not mandatory all other tumor biopsies will be strongly encouraged. A core tissue biopsy may be required at baseline if no leftover tissue is available for screening, tissue is older than 1 year, or there is not enough tissue for testing. Tumor biopsies may be performed at baseline (pre-treatment), Cycle 1 Day 15, and at the time of progression/EOT (where feasible).

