Dose Level -1	M6620: 120 mg/m  , QW, IV; Avelumab: 800 mg, Q2W, IV

**Note:** other intermediate doses of M6620 may be considered following discussion with EMD Serono.

When avelumab and M6620 are to be administered on the same day, avelumab will be administered first, with an interval of at least 1 hour between infusions.

[figure not shown]

Figure 2: Dose Expansion of the combination of M6620 and avelumab (Arm A)

Interim Analysis for Safety: Patients can have any qualifying DDR aberration for interim safety analysis. We will stop if, at any time during the study, we determine that there is more than an 80% chance that the posterior probability of toxicity (i.e., DLT) is more than 30%.

2Interim Analysis for Futility: Using a 3-stage design with 10 patients in each stage, we will stop after the 1st stage if we see 0 successes in 10 patients, after the 2nd stage if we see <2 successes in 20 patients, and we will declare the treatment worthy of further study if we see >3 successes in 30 patients. If we set p0 (highest success rate for unacceptable treatment) =5% and p1 (lowest success rate for acceptable treatment) =20%, this design has alpha=5%, 80% power and probability of early termination under p0 of 60% after 1st stage and 79% after either 1st or 2nd stage.

Note: This study will not be rejected for efficacy until at least N=10 patients with ATM variants have been evaluated for efficacy.

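### Section 3.5 names the next lowest dose level the MTD with no minimum number treated there, which conflicts with the six-patient MTD definition when level 1 cleared on 0/3

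*Combined protocol and SAP*

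**What the plan says.** The MTD definition appears twice. Section 3.4 asks for "less than 2 patients with DLT out of at least 6 patients at the dose level". Section 3.5 repeats it: "The MTD is defined as the highest dose level with less than two patients with DLT out of at least six patients".

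Section 3.5 also sets the pace of escalation: the decision to move up "will be made after the first 3 patients in a dose level have completed 28 days". Its stated trigger for adding three patients is a DLT at that same level. Section 3.4 is a little wider and fills a level to six "in the event that a DLT is observed in 1 of the first 3 patients and/or additional safety data are needed".

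Section 3.5 then closes with a de-escalation rule. The trigger is "If at any time, at least one third of the participants at a dose level (33%) experience DLTs". The action is that "the MTD will be reassessed and the next lowest dose level will be considered the MTD".

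Three dose levels are planned. Study Calendar footnote 16 says "M6620 may be administered to patients in the dose escalation phase at 1 of 3 doses" (240, 480 or 120 mg/m²), and the note under Table 1 in Section 3.2.1 adds that "other intermediate doses of M6620 may be considered". Section 9.3 plans 3-6 patients per dose level. The synopsis gives 3-6 for dose escalation and up to 36 in total.

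**The concern.** The closing sentence of Section 3.5 fixes the MTD by position (one level down) and the definition fixes it by evidence (six patients, fewer than 2 DLTs). The two agree only if the lower level already has six patients. A level that cleared on 0/3 has three, and nothing in the text requires the other three once the higher level fails. Two teams holding the same data could both follow Section 3.5, one declaring level 1 the MTD and the other saying it does not yet qualify.

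Establishing the MTD and RP2D is the second primary objective, and up to 30 expansion patients follow at the RP2D. The rule that ends escalation should therefore have one reading.

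**Working it through.** The plan states no operating characteristics for the escalation phase, so there is no figure of its own to reproduce. The decision rules come from Sections 3.4 and 3.5. The true DLT rates are assumptions, because the documents give none by dose level. Three patients are assumed to be enrolled first at each level; Section 3.4 permits three to six.

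**Do the DLT cut-offs agree?** At six patients, yes: 2/6 meets the one-third trigger, and 1/6 meets the definition. The conflict is about the number treated at the lower level. One loose end is that 1/3 also meets the trigger literally, although the sentence before it answers a DLT among three patients by adding three more. The main calculation follows that sentence.

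**Formulas.** Let p1 and p2 be the DLT rates at levels 1 and 2.
- Level 1 clears on three: (1−p1)³
- Level 1 clears on six (1/3, then 0/3): 3·p1·(1−p1)⁵
- Level 2 fails: P(≥2 of 3) + P(1 of 3) × P(≥1 of the next 3)
- Three more patients at level 1 reject it: P(≥2 of 3) at p1, since 0/3 plus two or more makes at least 2/6

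| Assumed p1 / p2 | 10% / 30% | 20% / 40% | 30% / 50% |
|---|---|---|---|
| Level 1 clears on 0/3 | 0.729 | 0.512 | 0.343 |
| Level 2 fails | 0.506 | 0.691 | 0.828 |
| Both (product) | 0.369 | 0.354 | 0.284 |
| Level 1 clears by either route and level 2 fails | 0.458 | 0.489 | 0.409 |
| Share of these with only three at level 1 | 0.80 | 0.72 | 0.69 |
| Three more patients reject level 1 | 0.028 | 0.104 | 0.216 |
| Rejected, as share of all trials | 0.010 | 0.037 | 0.061 |

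The last row is the third row times the sixth: 0.369 × 0.028, 0.354 × 0.104 and 0.284 × 0.216.

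**Sensitivity.** If a single DLT among the first three at level 2 already triggered the closing sentence, level 2 would fail with probability 1−(1−p2)³ = 0.657, 0.784 and 0.875. The affected path would then be 0.479, 0.401 and 0.300 of trials, and level 1 would be rejected on filling in 0.013, 0.042 and 0.065.

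**Precision.** The one-sided 95% Clopper-Pearson upper bound on the DLT rate is 63% after 0/3, 39% after 0/6 and 58% after 1/6. The last is the worst six-patient result that the definition accepts.

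**Would a toxic level 1 be caught later?** Suppose level 1 is named the MTD on 0/3 and two of the next three patients there have DLTs. The count is 2/6, which meets the one-third trigger. These are the same outcomes on which filling to six would reject level 1. The expansion rule in Section 9.6 (stop at 5/10 or 8/20) adds a partial check: Table 7 gives early stopping probabilities of 0.05, 0.28 and 0.63 at true toxicity of 20%, 30% and 40%.

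**The case against.** The best defence is that the text can be read without conflict. The six-patient definition is stated twice. Section 3.4 enrols six when more safety data are needed, and a level with three patients under a six-patient definition arguably needs them. The closing sentence speaks of reassessment, and the SMC must approve any change of dose level. Figure 4, which carries the escalation rules, is not shown in the copy reviewed and may contain the filling step.

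This reading is sensible, but those provisions permit the step and do not require it. The need for more data is a judgement that is not tied to failure of a higher dose. Reassessment is followed at once by a fixed outcome. SMC approval sets no minimum number. If Figure 4 has the step, the closing sentence still contradicts it. The unseen figure is a reason for caution and not itself a fault in the plan.

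The objection on size stands. The one-third trigger works at any time, the SMC reviews each dose-level summary, and the RP2D also draws on expansion data. Filling level 1 to six therefore mainly changes when the check is made.

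Two stronger readings are tempting. A reader might infer that the 28-37% is the chance of choosing a wrong dose, or that a toxic level 1 would pass into expansion unchecked. It is only the chance of meeting the conflict, and the safeguards above apply afterwards. A reader might also infer that, if starting level 1 fails, level −1 becomes the MTD with nobody treated there. The sentence taken literally says so, but footnote 16 lists level −1 as an escalation dose and Section 9.3 enrols 3-6 at each level. The point does not rest on that reading.

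**Conclusion.** The inconsistency is real and should be fixed. On the path where level 1 clears on 0/3 and level 2 fails, the closing sentence of Section 3.5 and the definition in Sections 3.4 and 3.5 give different answers. At the assumed rates this path takes 28-37% of trials, and it covers 69-80% of the cases in which level 1 clears and level 2 fails. In the remainder level 1 already stands at 1/6 and the two rules agree.

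The consequence is limited. Filling level 1 to six would reject it in about 1-6% of all trials, and the existing safeguards would probably catch many of those later. In the other affected trials the fix only supplies the six patients the plan already asks for. The benefit is one unambiguous rule, applied before the MTD is declared and expansion starts.

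The sizes depend on assumed DLT rates and on three patients being enrolled first at each level. Confidence is medium because Figure 4 could not be read.

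**What to change.** Keep the one-third trigger, acting at any time, as the rule for stopping enrolment at a level. State that 1 DLT in the first 3 leads to three more patients and not to de-escalation. Replace the ending of the sentence with:

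> *The next lowest dose level becomes the candidate MTD. If fewer than six DLT-evaluable patients have been treated there, it is enrolled or expanded to six, and it is declared the MTD only if fewer than 2 of those six have a DLT (3.4). If no level meets this, no MTD is declared and the SMC decides.*

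Add that, after declaration, the existing one-third trigger and the Section 9.6 rule govern further patients. A later count of 2/7 or 2/8, which is below one third, then has a defined status. Make Figure 4 agree.

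**Cost.** Up to three more patients at level 1, up to six more at level −1 if level 1 is then rejected, and one or more further 28-day windows. Counting every fill in full, the average is 3 × P(affected path) + 6 × P(level 1 rejected): 1.17, 1.28 and 1.22 patients per trial at the three assumed rate pairs.

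This fits the 3-6 per level of Section 9.3, but the synopsis counts need aligning. Six at level 1, 3-6 at level 2 and 30 in expansion make 39-42, or 45-48 with six at level −1, against a stated maximum of 36. That maximum is already tight: two levels of three plus 30 reach it exactly.

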#### 4. PATIENT ELIGIBILITY CRITERIA

This study can fulfill its objectives only if appropriate patients are enrolled. The following eligibility criteria are designed to select patients for whom participation in the study is considered appropriate. All relevant medical and non-medical conditions should be taken into consideration when deciding whether a particular patient is suitable for this protocol.

#### 4.1 Inclusion Criteria

Patients must meet all of the following inclusion criteria to be eligible for enrollment in the study.

- 1. Age ≥18 years.
- 2. Subjects must have histologically confirmed malignancy that is metastatic or unresectable and for which standard curative measures do not exist or are no longer effective.
- 3. Subjects will be eligible for this study based on the presence of actionable aberrations in one or more of the following DNA Damage Response (DDR) genes: ARID1A, ATM, ATR, ATRX, BAP1, BARD1, BRCA1/2, BRIP1, CDK12, CHEK2, FANCA, FANCC, FANCD2, FANCE, FANCF, FANCM, MRE11A, MSH2, NBN (NBS1), PALB2, RAD51, RAD51C, RAD51D, SMARCB1, and VHL, or other related genes at the discretion of the principal investigator in consultation with the MD Anderson Cancer Center Institute for Personalized Cancer Therapy Precision Oncology Decision Support (PODS) group. Variant interpretation for actionability will be performed by PODS.
- 4. Subjects with germline defects in DDR genes are eligible for this trial.
- 5. The collection of archival tumor tissue (within 1 year prior to study enrollment) will be mandatory. Tumor biopsies on Cycle 1 Day 15 will be mandatory. Subjects will not be put at undue risk to obtain the biopsy at C1D15. A biopsy at C1D15 will not be required if it poses a serious/severe complication risk greater than 2%. All other biopsy timepoints are not mandatory but will be strongly encouraged where feasible. These include at baseline and at disease progression. Archival and fresh tissue requests can be waived in exceptional circumstances with PI approval and only where rationale is documented.
- 6. Subjects must have received at least 1 line of systemic therapy in the advanced/metastatic setting. Subjects with diseases without known effective options, and subjects who had declined standard of care therapy prior to study introduction are also eligible.
- 7. Subjects enrolling in the dose escalation should have progressed on or be intolerant to all therapies known to confer a clinical benefit. Subjects must not have refused all available therapies.
- 8. Subjects who have received prior therapy with immune checkpoint inhibitors (ICIs) are eligible for this trial. Subjects with a standard-of-care option for an Immune Checkpoint Inhibitor are eligible.
- 9. Subjects must have measurable disease per RECIST v1.1, or patients may have bone metastatic disease evaluable by Prostate Cancer Working Group 3 (PCWG3) for subjects with metastatic castration-resistant prostate cancer (CRPC), or according to tumor evaluation criteria best suited and accepted for the tumor type to be evaluated.
- 10. Subjects must have an Eastern Cooperative Oncology Group (ECOG) performance status 0-1.
- 11. Subjects must have a life expectancy ≥12 weeks.
- 12. Subjects must have normal organ and marrow function as defined below:

- a. Absolute neutrophil count  $\geq 1.5 \times 10^9 / L$ ;
- b. Platelets ≥100 x 10^9/L:
- c. Hemoglobin  $\geq$  9 g/dL or  $\geq$  5.6 mmol/L
- d. Total bilirubin ≤1.5X the institutional upper limit of normal (ULN);
- e. AST(SGOT)/ALT(SGPT) ≤2.5X institutional ULN or ≤5X institutional ULN in the presence of liver metastases;
- f. Renal function defined by serum creatinine ≤ 2X ULN or estimated creatinine clearance ≥30 mL/min according to the Cockcroft-Gault formula.
- 13. Female patients of childbearing potential must have a negative serum or urine pregnancy test at screening (and again at baseline just prior to first administration of study drugs).

Female patients of non-childbearing potential must meet at least 1 of the following criteria:

- Achieved postmenopausal status, defined as follows: cessation of regular menses for at least 12 consecutive months, with no alternative pathological or physiological cause;
- b. Have undergone a documented hysterectomy and/or bilateral oophorectomy;
- c. Have medically confirmed ovarian failure.

All other female patients are considered to be of childbearing potential.

- 14. Women of childbearing potential and fertile men must agree to use adequate contraception when sexually active from signing of the informed consent form for the full study until at least 6 months after the last study drug administration. Patients must agree to utilize 2 reliable and acceptable methods of contraception simultaneously. A man is considered fertile after puberty unless permanently sterile by bilateral orchiectomy. Men taking part in this study are advised not to father a child during and up to 6 months after treatment; prior to treatment, advice should be sought for conserving sperm due to the chance of irreversible infertility as a consequence of treatment. Female partners of childbearing potential from male study patients have to use adequate contraception / birth control between signing of the informed consent and 6 months after the last administration of the study drug if the male study patient is not sterilized. The investigator or a designated associate is requested to advise the patient how to achieve highly effective birth control. Highly effective (failure rate of less than 1% per year) contraception methods, when used consistently and correctly, include:
  - Combined (estrogen and progestin containing: oral, intravaginal, transdermal) and progestin-only (oral, injectable, implantable) hormonal contraception associated with inhibition of ovulation.
  - Intra-uterine device or intrauterine hormone-releasing system.
  - Bilateral tubal occlusion or vasectomized partner (provided that partner is the sole sexual partner and has received medical assessment of the surgical success).
  - Sexual abstinence (reliability to be evaluated in relation to the duration of the clinical trial and the preferred and usual lifestyle of the patient).

Male patients with a female partner of reproductive potential must use a condom and ensure that an additional form of contraception is also used during treatment and until 6 months after last study drug administration. Patients must agree to utilize 2 reliable and acceptable methods of contraception simultaneously.

- 15. Evidence of a personally signed and dated informed consent document indicating that the patient has been informed of all pertinent aspects of the study.
- 16. Willing and able to comply with scheduled visits, treatment plan, laboratory tests, and other procedures.
- 17. Human Immunodeficiency Virus (HIV)-infected (HIV1/2 antibody-positive) patients may participate IF they meet all the following eligibility requirements:
  - a. They must be on an anti-retroviral regimen with evidence of at least two undetectable viral loads within the past 6 months on this same regimen; the most recent undetectable viral load must be within the past 12 weeks.
  - b. They must have a CD4 count ≥250 cells/mcL over the past 6 months on this same anti-retroviral regimen and must not have had a CD4 count <200 cells/ mcL over the past 2 years, unless it was deemed related to the cancer and/or chemotherapy-induced bone marrow suppression.
    - i. For patients who have received chemotherapy in the past 6 months, a CD4 count <250 cells/mcL during chemotherapy is permitted as long as viral loads were undetectable during this same chemotherapy.
  - c. They must have an undetectable viral load and a CD4 count ≥250 cells/mcL within 7 days of enrolment.
  - d. They must not be currently receiving prophylactic therapy for an opportunistic infection and must not have had an opportunistic infection within the past 6 months.

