# 9.1.3 Response Analysis Set

All enrolled patients who receive at least one (1) dose of study medication with baseline assessment and have at least one post-baseline tumor assessment will be considered evaluable for response.

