# 9.5 Efficacy Analysis

The efficacy population will consist of all patients who receive at least one dose of study medication with baseline assessment and have at least one (1) post-baseline tumor assessment. This population will be used for primary analyses of efficacy.

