# 9.5.1 Efficacy Evaluation

Clinical efficacy will be measured by clinical benefit rate (CBR) per RECIST v1.1 and irRECIST. CBR is defined as complete response (CR) + partial response (PR) + stable disease (SD) > 6 months. Overall response rate (ORR) will be measured using RECIST 1.1 criteria. Secondary efficacy endpoints include objective response (CR+PR), progression free survival (PFS), Duration of Response (DoR), overall survival (OS) and ORR. A 95% CI of response rate will be estimated based on the binomial distribution.

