# Appendix D: Assessment of Radiographic Response and Progression in Patients with CRPC

Radiographic imaging for patients with CRPC is categorized as soft tissue or bone. Soft tissue imaging may include CT scans of the chest, abdomen and pelvis or MRIs of the abdomen and pelvis). Bone imaging including a whole body radionuclide bone scan (scintigraphy) is required at baseline and at regular image screening intervals in all patients with prostate cancer enrolling on trial.

The investigator will assess response of soft tissue disease by RECIST v1.1 (see Appendix 16.2). However, bone disease will not be considered as non-target lesions assessed by RECIST v1.1. An objective response is defined as a best overall response of CR or PR per RECIST v1.1 and must be confirmed on repeated imaging at least 4 weeks after initial documentation. Bone disease will be assessed for progressive disease only by PCWG3.64. The documentation required for the determination of radiographic progression is shown in the table below.

Date Progression Detected a	Criteria for Progression	Criteria to Confirm Progression	Criteria to Document Disease Progression on Confirmatory Scan
Week 8	Bone lesions: 2 or more new lesions compared to screening bone scan by PCWG3	Timing: At least 6 weeks after progression identified or at Week 16 visit b	2 or more new bone lesions on bone scan compared to Week 8 scan
	Soft tissue lesions: Progressive disease on CT or MRI by RECIST v1.1	No confirmatory scan required for soft tissue disease progression	No confirmatory scan required for soft tissue disease progression
Week 16 or later	Bone lesions: 2 or more new lesions on bone scan compared to Week 8 bone scan	Timing: At least 6 weeks after progression identified or at next imaging time point b	Persistent or increase in number of bone lesions on bone scan compared to prior scan c
	Soft tissue lesions: Progressive disease on CT or MRI by RECIST v1.1	No confirmatory scan required for soft tissue disease progression	No confirmatory scan required for soft tissue disease progression

- Progression detected by bone scan at an unscheduled visit either before Week 8
  or between scheduled visits will require a confirmatory scan at least 6 weeks later
  and should follow confirmation criteria outlined in the table for the next scheduled
  scan.
- Confirmation must occur at the next available scan.

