# Confirmatory Imaging Requirements for Patients with mCRPC Based on RECIST v1.1 and PCWG3

Disease Site	Response	Progression a
Soft tissue	Must be confirmed at least 4 weeks later	No confirmation required
Bone	Not applicable	Must be confirmed at least 6 weeks later

a To inform permanent treatment discontinuation.

Radiographic PFS is defined as the time from the start of treatment to documentation of radiographic progression in soft tissue by investigator' assessment according to RECIST v1.1, in bone by investigator's assessment according to PCWG3, or death if within 2 tumor assessments after last completed tumor assessment, whichever occurs first.

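### Castration-resistant prostate cancer (CRPC) patients with bone-only disease count in the ORR denominator but cannot be RECIST 1.1 responders, so case mix dilutes the reported ORR

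*Combined protocol and SAP*

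**What the plan says.** **Eligibility.** Inclusion criterion 9 (4.1) gives three alternatives: RECIST 1.1 measurable disease; for CRPC, "patients may have bone metastatic disease evaluable by Prostate Cancer Working Group 3 (PCWG3"); or disease assessable by whatever criteria suit the tumor type. The second, and possibly the third, admits patients with no measurable lesion.

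**Denominator.** Under 9.1.3, treated patients "with baseline assessment and have at least one post-baseline tumor assessment will be considered evaluable for response". Section 9.5 defines the efficacy population in the same way and adds: "This population will be used for primary analyses of efficacy". Neither requires measurable disease.

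**Scoring.** Section 9.5.1 states: "Overall response rate (ORR) will be measured using RECIST 1.1 criteria". For CRPC, Appendix D says that "bone disease will not be considered as non-target lesions assessed by RECIST v1.1", limits the PCWG3 bone assessment to progression, and adds: "An objective response is defined as a best overall response of CR or PR per RECIST v1.1". In its confirmatory imaging table, the response entry for bone is "Not applicable".

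**Decision rule.** Section 9.3 sets three stages of 10 evaluable patients. The trial stops at 0 of 10 or fewer than 2 of 20 successes and is positive above 3 of 30, with p0 = 5%, p1 = 20%, alpha 5% and power 80%. It does not say whether a success is an objective response or clinical benefit.

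**The concern.** Taken together, these sections let a patient in, call that patient evaluable for response, and provide no way for a response to be recorded. Each such patient adds one to the ORR denominator and can never add to the numerator. The reported ORR then depends partly on how many bone-only CRPC patients enrolled, which says nothing about activity. No section removes these patients, caps their number, or plans an ORR in measurable patients only.

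A related gap concerns CBR, which counts SD beyond 6 months. Appendix B defines SD through target lesions and Appendix C through sums of lesion diameters. Nothing says whether a bone-only patient without PCWG3 progression for more than 6 months has SD. If that patient does not, the same dilution reaches CBR.

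**Working it through.** **1. Can a bone-only CRPC patient be a RECIST 1.1 responder?** PR needs a 30% fall in the sum of target-lesion diameters, and there are no target lesions. CR through non-target disease is closed, because Appendix D takes bone out of the non-target category in CRPC. The overall-status table in Appendix B covers only patients with measurable disease at baseline. The answer under Appendix D is no.

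**2. Dilution of ORR.** Let r be the true ORR in measurable patients and m the number of bone-only patients among 30. Expected reported ORR = r × (30 − m)/30. I take r = 20%, the plan's p1, for illustration. The values of m are assumptions.

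| m of 30 | Expected ORR |
|---|---|
| 0 | 20.0% |
| 1 | 0.20 × 29/30 = 19.3% |
| 3 | 0.20 × 27/30 = 18.0% |
| 6 | 0.20 × 24/30 = 16.0% |

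**3. The same data under the two denominators.** Take 6 responders, with exact (Clopper-Pearson) 95% intervals:

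- 6/30 = 20.0% (7.7 to 38.6)
- 6/27 = 22.2% (8.6 to 42.3), with 3 bone-only patients removed
- 6/24 = 25.0% (9.8 to 46.7), with 6 removed

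**4. The plan's own operating characteristics.** I used an exact binomial calculation: continue with at least 1/10 and at least 2/20, positive with at least 4/30. At p = 0.05 the probability of a positive result is 0.049, with early termination 0.599 after stage 1 and 0.787 after stage 1 or 2. At p = 0.20 power is 0.805. These agree with the stated 5%, 60%, 79% and 80%.

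**5. Conditional effect on the stage rules.** This step applies only if success means objective response, or if success means CBR and bone non-progression does not count as SD. Bone-only patients then contribute zero successes, and the remaining patients in each stage have p = 0.20.

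| m of 30 | Patients per stage who can succeed | Power | Futility stop at stage 1 or 2 when p = 0.20 |
|---|---|---|---|
| 0 | 10, 10, 10 | 80.5% | 13.6% |
| 1 | 9 in one stage, 10 in the others | 77.0% to 79.4%, depending on the stage | 13.6% to 16.7% |
| 3 | 9, 9, 9 | 74.0% | 17.5% |
| 6 | 8, 8, 8 | 65.7% | 22.4% |

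Applying the diluted rate to all 10 patients per stage instead gives 78.4% (p = 0.193), 73.5% (p = 0.18) and 64.7% (p = 0.16), within about a point. Alpha falls too, from 4.9% to 3.5% (m = 3) and 2.4% (m = 6), so the error is toward a negative result.

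**The case against.** - **ORR is a descriptive secondary endpoint.** The primary endpoints are adverse events and DLTs, and counting every assessed patient is conservative. That limits the consequence. It does not make a patient with no scorable response informative about the response rate.
- **There may be few such patients, or none.** Eligibility spans all solid tumors and more than 20 genes. Section 7.3, on palliative radiation, and 7.4, on biopsy of target lesions, are written as if patients have several target lesions. This stands: the size is unknown and may be zero. CRPC enrolment is nonetheless provided for, in 5.4.10, in the prostate bone scans of 7.3 and throughout Appendix D.
- **irRECIST leaves a route open.** The secondary endpoints in 2.2.1 also list ORR by irRECIST, and Appendix C defines its complete response over all lesions, measurable or not. A reader might infer that bone-only patients cannot respond under any criterion. The documents do not support that; the statement is strict only for RECIST 1.1. Still, 9.5.1 measures ORR by RECIST 1.1, and Appendix D gives CRPC no irRECIST route.
- **Section 7.3 lists bone lesions as non-target.** On that text alone, a CR by disappearance of non-target disease would be conceivable, though not a PR. Appendix D says otherwise for CRPC. The two sections conflict, and the conflict does not answer the point.
- **Success probably means CBR.** Section 9.5.1 names CBR as the measure of clinical efficacy, and it is the first secondary objective. If bone non-progression beyond 6 months counts as SD, the power loss in step 5 does not arise. This objection stands and is why those figures are conditional.

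**Conclusion.** The point holds for RECIST 1.1 ORR. Any bone-only CRPC patient in the Response Analysis Set is a non-responder by construction, and the bias is downward. At a true 20% in measurable patients, the expected loss is 0.7 percentage points with 1 of 30 bone-only, 2 with 3 and 4 with 6. It is nil if none enrol. The counts are assumed throughout.

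A reader might infer that the go/no-go rule is underpowered as written. The documents do not establish that. Success is undefined, 9.5.1 leans toward CBR, and the treatment of bone non-progression is unstated rather than excluded. The fall from 80.5% to about 78%, 74% and 66% is what would follow if success meant objective response, or if bone non-progression were not SD. Changing the ORR denominator would not by itself alter the stage rules.

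This is a modest clarification of a secondary analysis. It is best made before results are seen, because choosing between 6/30 and 6/24 afterwards would be data-driven.

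**What to change.** 1. In 9.1.3 and 9.5, define the ORR denominator as patients with RECIST 1.1 measurable disease at baseline, otherwise meeting the present criteria, and use the same set for DoR. This also covers patients without measurable disease who enter through the third option of inclusion criterion 9.
2. Keep bone-only patients in the CBR, PFS and OS analyses.
3. In 9.5.1, state how absence of PCWG3 progression beyond 6 months counts as SD for CBR.
4. In 9.3, name the endpoint that counts as a success, and use the matching evaluable set for the stage counts of 10, 20 and 30.
5. Reconcile 7.3, which lists bone lesions as non-target, with Appendix D, which does not treat them so in CRPC.

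The cost is SAP and protocol wording, a slightly smaller ORR denominator and a slightly wider interval: with 6 responders, the width goes from 30.9 points (6/30) to 33.7 (6/27). If success is defined as objective response, counting stages in measurable patients means that bone-only patients no longer fill stage places, and the stated accrual limit of 36 should be checked against that. Eligibility and treatment are unchanged.
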